Research question: Can implementation of an evidence based educational intervention, focussed on accurate diagnosis of appendicitis, safely reduce unnecessary admissions to hospital in patients with suspected appendicitis?

Background: Acute appendicitis is one of the most common surgical emergencies. Over 55,000 operations for appendicitis are performed each year in the UK. However, a significant proportion of patients with right iliac fossa (RIF) pain are misdiagnosed and placed on incorrect care pathways. Most of these patients receive unnecessary hospital admissions for monitoring and do not undergo an intervention. Some admissions result in patients receiving a negative appendicectomy, exposing them to unnecessary pain and complications. Furthermore, this leads to delayed treatment for the underlying condition they initially presented to hospital with.

Aim: To improve right iliac fossa care pathways by reducing unnecessary admissions to hospital.

Design: Multicentre, parallel cluster randomised controlled trial with an effectiveness-implementation design. This type of trial combines elements of both implementation and effectiveness research to address the real-world effectiveness of an intervention while also considering how well it can be implemented in practice. Each cluster corresponds to an acute care hospital.

Eligibility: Any hospital in the UK providing an acute general surgery service. Additionally, the hospital must have the ability to admit patients overnight and to schedule follow up in the surgical admissions unit or ambulatory clinic.

Participants: Members of the acute surgical team involved in the assessment of patients with RIF pain and suspected appendicitis.

Population: Data from hospital notes will be collected from consecutive patients aged 16 to 39 years old (inclusive) attending hospital with right iliac fossa pain over an 8-week period.

Intervention: The intervention is the CLARITY accurate diagnosis package, which is made up of three components: the evidence based education programme (EBP), an implementation checklist and local implementation strategies. The EBP is considered the main component of our intervention and will be delivered using a digital education platform to intervention sites.

Comparison: Routine clinical care (sites without CLARITY EBP).

Primary Outcome: Non-operative admission rate (NOAR) - defined as unnecessary overnight admission.

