There is a significant gap between the publication of research and its widespread integration into practice. Although the efficacy of many interventions in perioperative and surgical care are well-established, there is a difficulty in translating these interventions into the emergency setting. Although many pragmatic trials looking at intervention effectiveness have had promising results, they continue to be met with significant environmental and organisational barriers.

In this trial, we already know what the best evidence based practice for the diagnosis of appendicitis is. The main barrier to improving care is identifying methods of effectively implementing the evidence into practice, which this trial aims to do. We will assess the effectiveness of our intervention but also measure how effective implementation strategies are for facilitating its adoption. Currently, there are very few studies which have assessed implementation factors in the perioperative or surgical setting.

Therefore, there is a clear need for research into how we can implement best clinical practice effectively into the National Health Service (NHS) for patients with suspected appendicitis, with the aim of minimising unnecessary hospital admissions and unnecessary surgery.

Justification of patient population

We will include all consecutive patients aged between 16 to 39 (inclusive) years old who present with right iliac fossa pain to participating hospitals over a given 8-week period. This age group are at highest risk of developing acute appendicitis and being admitted to hospital unnecessarily. Other diagnoses are more important in patients aged 40 and over, namely right sided colorectal cancer. These patients should routinely receive standard CT scans and are at a much lower risk of receiving unnecessary admissions or operations since CT is very accurate for diagnosing acute appendicitis.

We will not include patients who have already had their appendix removed as they cannot develop appendicitis. We will also not include pregnant people in this study, as they should be cared for by obstetricians, rather than the emergency general surgery team.

Rationale for study design

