CLARITY is a multicentre, parallel cluster randomised controlled trial with a hybrid type II effectiveness-implementation design. This will assess both the implementation and effectiveness of our intervention. Our primary intervention is the evidence-based programme to improve diagnostic assessment in suspected appendicitis. However, we also assess the effectiveness of the CLARITY implementation strategies. Studying implementation strategies tailored to acute surgical teams is crucial to increasing the adoption of practice-changing interventions in emergency surgery.

CLARITY involves healthcare staff at the level of the hospital, not individual patients. Therefore, a cluster randomised trial is the most appropriate design (figure 1). We will study whether undertaking the CLARITY intervention increases the adoption of best-practice recommendations and whether this leads to an improvement in patient outcomes.

[figure not shown]
RESEARCH QUESTION

Can implementation of an evidence-based educational intervention, focused on the accurate diagnosis of acute appendicitis, safely reduce unnecessary admissions to hospital in patients with suspected appendicitis?

Trial design

The CLARITY trial is a multicentre, cluster randomised controlled trial using a hybrid type II implementation effectiveness design. Sites will be randomised using a 1:1 minimisation algorithm into three batches with a staggered start (see figure 2). CLARITY includes an internal pilot study.

Figure 2: Parallel cluster randomisation with staggering of sites across three start dates. Groups A+B are part of the internal pilot and include roughly 10 sites. The remaining groups will contain at least another 30 sites between them.

TRIAL OBJECTIVES

Pilot study objectives

We aim to conduct a pilot study assessing the feasibility of a full phase trial, measured by site recruitment, uptake of our intervention and collection of primary outcome data. This includes the following objectives:

- Open at least 9 sites, with a mix of rural, district general and tertiary centres
- Accrual of data from a minimum of 100 patients over 8 weeks
- Sufficient uptake of the intervention by local participants

Main trial objectives

 To determine whether implementation of the CLARITY evidence-based programme can reduce non-operative admission rates

Secondary objectives

- To determine whether implementation of the CLARITY evidence-based programme can reduce unnecessary surgeries and improve patient outcomes

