- To assess the effectiveness of the CLARITY implementation strategy on increasing uptake of the intervention and adherence to evidence-based recommendations in the emergency surgery setting

ELIGIBILITY

Hospital inclusion criteria

- Any hospital in the UK providing emergency general surgical services
- The ability to schedule patients for a follow up assessment in the surgical admission unit or ambulatory/hot clinic service

Participant inclusion criteria

- Doctors and clinicians assessing patients with RIF pain, within the acute surgical team
- This includes consultants, specialty doctors, registrars, senior house officers, foundation doctors, surgical nurse practitioner and physicians associates

Patient inclusion criteria

All patients aged 16 to 39 (inclusive) years old attending hospital with right iliac fossa pain

 AND under the care of the general surgery team, including in the emergency department, surgical admissions unit, or paediatrics ward.

Patient exclusion criteria

- Previous appendicectomy
- Current pregnancy
- Patients with RIF pain under the care of secondary teams

Each patient should only be included in CLARITY once. Following the index assessment included in CLARITY, patients undergoing additional assessments within the study window should not be included for a second time. Readmission is captured as a study outcome.

If patients with right iliac fossa pain are subsequently found to have an alternative diagnosis or pathology causing the pain, they must still be included in the study and followed up.

Selection bias

Selection bias will be closely monitored by the Study Management Group. CLARITY trial coordinators will regularly liaise with site Principal Investigators to ensure that all eligible patients are entered. Recruitment rates will be monitored across individual sites and clarification will be sought in case of a drop in recruitment which might indicate that eligible patients are not being included. An independent validation process will monitor case ascertainment (see *Monitoring* and *Data Validation*).

PATIENT IDENTIFICATION

Each hospital will decide how best to identify eligible patients in their own patient pathways.

As guidance, it is anticipated that patients may be identified from any of the following settings, as long as their attendance or admission start date falls within the trial data collection period:

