Local implementation strategies: a guide for local facilitators that focuses on environmental implementation strategies. It was developed using results of a national survey of acute surgical teams. It includes a graded strategy system to promote uptake of the education package and to support implementation of its evidence-based recommendations. All participating sites will be asked to report the level of implementation of the proposed strategies.

[figure not shown]
The CLARITY evidence-based education programme

The EBP is an online educational intervention containing six modules:

- 1. Introduction to the anatomy and pathophysiology of appendicitis and how to manage risk which evolves over time
- 2. Discussion on the meaning of evidence and how to use it in clinical practice
- 3. Patient-level risk stratification of appendicitis for RIF pain, focusing on the management of low-risk patients
- 4. Patient-level risk stratification of appendicitis for RIF pain, focusing on the management of medium- and high-risk patients
- 5. Communication with patients and colleagues (implementation)
- 6. Summary of the EBP

Intervention timing

Figure 3: Illustrates the timeline for site recruitment and participation.

Sites will be randomised to either receive the CLARITY intervention or usual care once all site approvals have been confirmed. A minimisation algorithm will be used which will allow for sites to be sequentially randomised once ready. The data collection window will take into account changeover in clinical placements for doctors. If the trial is not completed within a single rotation, doctors who have received the CLARITY package could move from sites which received the intervention to sites which did not receive the intervention, thereby contaminating the results. We will monitor and try to minimise this effect as much as possible.

To ensure that the study is attractive for potential collaborators to participate, all hospitals will have access to the CLARITY accurate-diagnosis package at the end of the trial.

Training platform

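### The secondary objective on the implementation strategy's effect on uptake has no randomised comparator; the trial can only describe uptake and compare adherence for the package as a whole

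*Protocol*

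**What the plan says.** The Protocol, Trial Objectives (Secondary objectives), sets the aim "To assess the effectiveness of the CLARITY implementation strategy on increasing uptake of the intervention and adherence to evidence-based recommendations". The same intention appears in three other places. The section on the need for implementation research in surgery says the trial will "measure how effective implementation strategies are for facilitating its adoption". Rationale for study design and Study Intervention both say that the effectiveness of the strategies will be assessed in addition to that of the education programme.

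The summary describes the intervention as a package "which is made up of three components: the evidence based education programme (EBP), an implementation checklist and local implementation strategies". The comparator is "Routine clinical care (sites without CLARITY EBP"). Under Intervention timing, "Sites will be randomised to either receive the CLARITY intervention or usual care once all site approvals have been confirmed", and control hospitals are given the package when the trial is over.

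On measurement, the description of the package says that the strategies are graded and that sites report how far they put them in place. CLARITY Champions and Training says that the modules are password protected, so that compliance can be followed in the experimental arm, and that completion is monitored by centre. The pilot STOP-GO criterion on uptake is 50% completion among intervention-arm participants.

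**The concern.** Effectiveness in increasing uptake is a comparative idea: it asks how much higher uptake is with the strategies than it would have been without them. The design contains no hospital in which the EBP is offered without the strategies, so the second half of that comparison is never observed.

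At stake is what the trial may conclude. If the objective is followed as worded, either completion in a single arm or a non-randomised association would stand as the effectiveness of the strategy. The Protocol itself says that few surgical studies have looked at implementation, so such a conclusion could carry weight. A service deciding whether to fund local facilitation as well as the e-learning would be relying on a contrast that the trial did not make.

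**Working it through.** The question is structural: which effects do the two arms identify? No sample-size figure in the Protocol bears on it.

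**Step 1. Lay out the cells.** Inputs: the package definition (summary; Study Intervention), two-arm 1:1 allocation by hospital (Intervention timing; Trial design), and 20 clusters per arm (Sample Size).

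| | Strategies offered | Strategies not offered |
|---|---|---|
| EBP offered | 20 hospitals | 0 hospitals |
| EBP not offered | 0 hospitals | 20 hospitals |

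The three-batch staggered start does not fill an empty cell. It changes when a hospital starts, not what it is offered.

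**Step 2. Uptake.** Write U for the EBP completion rate. The objective needs

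strategy effect = U(EBP with strategies) − U(EBP without strategies).

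The second term belongs to the cell with 0 hospitals. The randomised contrast is instead

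U(intervention arm) − U(control arm) = U(intervention arm) − 0,

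because control hospitals have no EBP to complete during the trial, apart from any contamination through rotating staff, which the Protocol tries to limit. That difference shows that the EBP was offered; it says nothing about the strategies.

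To illustrate, take completion of 50%, the pilot threshold, and let u be the unknown completion rate without the strategies. The strategy effect is 50 − u percentage points: +50 if u = 0, zero if u = 50, −50 if u = 100. The randomised contrast is 50 − 0 = 50 points in every case, so it cannot tell these apart.

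**Step 3. What can be estimated on uptake.** Sites report a level of strategy use and completion is tracked by centre. The two can be related across the intervention hospitals. The level is chosen and reported by the site, not allocated. A motivated team is likely both to apply more strategies and to complete more modules, so the relation mixes strategy effect with site engagement.

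**Step 4. Adherence.** Write A for adherence to the recommendations, which exists in both arms.

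A(intervention arm) − A(control arm) = effect of EBP, checklist and strategies together.

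This is a valid randomised contrast. It is one equation for three components, so it cannot be divided among them. The same holds for NOAR, where the main objective is worded as "To determine whether implementation of the CLARITY evidence-based programme can reduce non-operative admission rates" although what is randomised is the three-part package.

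**Step 5. Passages that might seem to disagree.** Training platform describes the e-learning as reachable by all participating sites, which alone would suggest that controls have access. Read with the comparator definition, the delayed access for controls and the password protection, access during the trial is confined to the intervention arm.

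**The case against.** Three points can be made for the Protocol.

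*The objective is not empty.* A reader might infer that nothing can be learned about strategy and uptake, or that the whole objective fails. The documents do not support that. Graded strategy use and centre-level completion give an observational estimate, and adherence can be compared between randomised arms. Rationale for study design already asks, at package level, whether the intervention raises adoption of best practice. This stands, and it limits the point to the causal reading of the uptake half and to the separation of components.

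*A hybrid type II trial need not randomise its implementation strategy, and the analysis plan is not shown.* The summary describes the design as also considering how well the intervention can be put into practice, which is compatible with a descriptive aim. A descriptive aim would be sound. The stated objective, however, speaks of effectiveness in increasing uptake. An analysis plan can choose estimators and label them honestly, but it cannot create a group that receives the EBP without the strategies.

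*The bundle is openly disclosed.* A reader might infer that the Protocol plans to credit any NOAR effect to the e-learning alone. It does not say so: it defines the package, names the EBP as the main component, and words the main objective around implementing the programme. Testing a bundle against usual care is a legitimate choice. A sentence on attribution would be a clarification, not the correction of an error.

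**Conclusion.** The point holds in limited form. The effect of the implementation strategy on uptake is not identified by the randomised comparison: by the plan's own numbers, 20 hospitals have the EBP with the strategies, 0 have it without, and 20 have neither. Only an observational association within the intervention hospitals is available. The adherence half of the objective is answerable as an effect of the package.

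This assumes that all intervention hospitals are offered the full package, as the summary and Study Intervention state, and that controls have no access before the trial ends. Randomisation, primary outcome, primary analysis, sample size and safety outcomes are untouched. The objective should be reworded because it determines what the trial may claim, but the defect does not threaten the main result.

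**What to change.** In Trial Objectives, and to match in the section on implementation research in surgery, Rationale for study design and Study Intervention, restate the aim in two parts:

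1. Describe EBP uptake and the reported level of strategy use in intervention hospitals, with any association between the two labelled observational and open to confounding by site engagement.
2. Compare adherence to evidence-based recommendations between arms as an effect of the whole CLARITY package.

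Add one sentence saying that between-arm effects, including that on NOAR, are effects of the package and cannot be apportioned to a single component.

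The cost is wording and a narrower conclusion: the sponsor gives up a causal claim about the strategy alone. No change to sites, data or design is needed, provided the case report form, which is not shown, records the items that define adherence. The Protocol says that investigations and management are collected.

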A particular concern with unnecessary admissions is that a proportion of patients, particularly those with longer hospital stays, undergo a negative appendicectomy.[3] An unnecessary appendicectomy carries the same rate of complications as surgery for true appendicitis.[4] Complications include wound infections, port site hernias, pain and unnecessary time away from their usual activities, such as work, education and caring.[2,5-6] In the UK, the negative appendicectomy rate (NAR) has consistently been found to be around 20%. This suggests there are up to 15,000 appendicectomies being performed annually for patients with a normal appendix. Hence, a large number of patients are exposed to harm from postoperative complications (7% of women and 23% of men).[2] In comparison to other European countries, the UK has a three-fold higher rate of unnecessary operations for appendicitis.[2]

Standardisation of pathways in right iliac fossa pain

There is significant variation in UK practice in the management of RIF pain, which leads to inappropriate selection of patients for imaging and surgery and results in suboptimal patient outcomes.[2-3] Our goal is to use education to standardise practice and encourage risk stratification and selective imaging in RIF pain. Evidence-based recommendations for diagnosing appendicitis exist but many healthcare professionals are not aware of them and they are rarely implemented in practice. Our primary intervention is an evidence-based programme to improve diagnostic assessment in suspected appendicitis. We also assess the effectiveness of the CLARITY implementation strategies in the emergency setting.

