 At time of attendance to hospital: Referrals made to the surgical team and/or emergency surgical admissions During admission: By the emergency surgical team or research team

Patients will be identified by a suitable person who may include:

- Any doctor involved in the patient's care (e.g. surgeon in training)
- Nurse practitioner or research nurse or members of the extended surgical team
- Medical students

Patients do not need to stay overnight or to be admitted to hospital to be eligible for inclusion in the study.

STUDY INTERVENTION

We will be delivering the CLARITY accurate diagnosis package across sites in the UK. Within this, *our main intervention* is the evidence-based programme to improve diagnostic assessment in suspected appendicitis. We will also assess the effectiveness of the CLARITY implementation strategies and access to tools and checklists.

The CLARITY accurate diagnosis package

The CLARITY accurate diagnosis package consists of an evidence-based education programme, an implementation checklist and implementation strategies. The package combines education with implementation science. It aims to provide an evidence-based learning programme around how to diagnose and manage appendicitis in a safe way which minimises unnecessary admission and surgery, whilst ensuring people with appendicitis receive prompt treatment. The content of the EBP is based on the latest evidence and provides education on how to provide 'gold-standard' care for patients with appendicitis. It does not involve any new interventions which would not be regarded as routine clinical care. The following describes the three components of CLARITY accurate diagnosis package in greater detail:

Evidence-based education programme: aimed at increasing the adoption of evidence based practice and reducing misdiagnosis, unnecessary admission and negative appendicectomy in suspected appendicitis. This intervention provides accessible information on how to calculate Version 1.0, Jan 7, 2024

the risk of acute appendicitis in people with right iliac fossa pain and choosing the best diagnostic imaging modality.

Implementation checklist: A summary of EBP recommendations and access to tools such as
prompts or checklists for participants to consider implementing within their practice. We will
capture data on whether these tools are useful or used in clinical practice.

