The primary outcome measure is the proportion of people admitted overnight with right iliac fossa pain, who do not undergo an operation. This is known as the non-operative admission rate (NOAR). A small minority of non-operative admissions on the suspected appendicitis pathways will be due to other acute GI pathologies treated by the general surgical team (e.g. diverticulitis, colitis, hepatobiliary, tumours of the appendix, small bowel or colon etc.). Furthermore, a few patients with simple appendicitis may be managed nonoperatively. According to RIFT study, these groups constitute around 3% of all RIF pain referrals. Our objective is to reduce the NOAR while accepting that a very small number of nonoperative admissions will remain necessary. We will measure the contribution of these groups to non-operative admissions.

Main Trial Secondary Outcome Measure

The secondary outcomes will describe the efficacy and safety of the CLARITY package. Of primary concern is safety, as the CLARITY trial seeks to test whether the EBP can reduce unnecessary appendicectomy, whilst maintaining safety. All outcomes in the main study should be measured up to 30 days from attendance/admission, with day 0 being the first day of attendance/admission.

The secondary safety outcomes will include:

- Proportion of patients that were not correctly diagnosed with appendicitis on their first hospital attendance and review by the surgical team (missed or delayed diagnosis)
- The proportion of patients with complicated appendicitis (phlegmon, abscess or perforation)

Version 1.0, Jan 7, 2024

- Days alive and out of hospital
- Readmission or re-attendance to hospital (including discharge from assessment unit and subsequent reattendance for appendicitis i.e. 'missed appendicitis')
- Radiological, percutaneous or endoscopic drainage
- Unplanned admission to critical care (Level 2/3 care)
- Mortality (both inpatient and in the community from any cause)

The secondary safety outcomes for patients who received an operation are:

- Proportion of patients with a negative appendicectomy (appendix normal on histopathological examination)
- Time from symptom onset to decision to operate and to skin incision (in hours)
- Surgical site infection, as defined by the Centers for Disease Control criteria
- Surgical complications, as measured using the Clavien-Dindo classification system
- Reoperation for any cause

CLARITY CHAMPIONS AND TRAINING

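### The primary outcome (overnight admission without any operation) does not match its label of unnecessary overnight admission: removal of a normal appendix counts as a non-event

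*Protocol*

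**What the plan says.** Protocol, Main Trial Primary Outcome Measure: NOAR is "the proportion of people admitted overnight with right iliac fossa pain, who do not undergo an operation". No condition is set on the type of operation or on histology.

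Protocol summary, Primary Outcome: "Non-operative admission rate (NOAR) - defined as unnecessary overnight admission".

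Two places put negative appendicectomy inside the admissions the trial wants to avoid. The summary background says "Some admissions result in patients receiving a negative appendicectomy, exposing them to unnecessary pain and complications". The Background and Rationale says "A particular concern with unnecessary admissions is that a proportion of patients, particularly those with longer hospital stays, undergo a negative appendicectomy".

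The education programme is aimed at "reducing misdiagnosis, unnecessary admission and negative appendicectomy in suspected appendicitis", and a secondary objective is to find out whether it "can reduce unnecessary surgeries and improve patient outcomes".

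The primary outcome section does discuss one gap between the measure and its intent: "Our objective is to reduce the NOAR while accepting that a very small number of nonoperative admissions will remain necessary". It puts these necessary non-operative admissions at around 3% of referrals and will measure their contribution. It does not mention the opposite gap, unnecessary admissions that end in an operation. Negative appendicectomy, judged on histology, is a secondary safety outcome listed for operated patients only.

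**The concern.** NOAR and the construct it is named after disagree about one group: patients admitted overnight whose removed appendix proves normal. In the rationale some of them are unnecessary admissions. In the endpoint none of them is an event.

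This matters because the programme targets both components. If a patient who would have had a normal appendix removed is instead observed overnight, the secondary objective has been met and NOAR gains an event. If an observed patient instead has a normal appendix removed, NOAR loses an event and no admission has been avoided. The decision to operate therefore settles the endpoint, and the Blinding section says the surgical team and outcome assessors know the allocation. A change in NOAR cannot by itself be read as a change in unnecessary admissions, which is how the summary would have it read.

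**Working it through.** **Inputs from the protocol**
- About 60% of patients admitted with suspected appendicitis receive no intervention (Background and Rationale).
- Negative appendicectomy rate about 20% (same section).
- 20 clusters per arm, 120 patients per cluster, ICC 0.06, α 0.05, power 0.90, 25% reduction, cluster size variation 50% (Sample Size).

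**Assumptions**
- The 25% is relative and the test two-sided.
- The 60% is the baseline NOAR; the Sample Size section gives none.
- All admitted patients who are not in the 60% have an appendicectomy.

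**1. Reproducing the stated power**
- Design effect = 1 + ((1 + 0.5²) × 120 − 1) × 0.06 = 1 + 149 × 0.06 = 9.94.
- Effective n per arm = 2400 / 9.94 = 241.4.
- Target: 0.60 to 0.75 × 0.60 = 0.45, a fall of 15 points.
- Power = Φ[(d − 1.96 × SE₀) / SE₁], where d is the difference, SE₀ = √(2p̄(1 − p̄)/n) and SE₁ = √((p₁(1 − p₁) + p₂(1 − p₂))/n).
- Here SE₀ = 0.0454 and SE₁ = 0.0449, so power = Φ(1.356) = 0.91. A t version with 38 degrees of freedom gives 0.90.

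The stated 0.90 is reproduced, so 60% is a fair working baseline. At baselines of 50%, 55% and 65% the same formula gives 0.79, 0.86 and 0.95.

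**2. Counts per 100 overnight admissions**
- Non-operative: 60. Operated: 40. Normal appendix: 0.20 × 40 = 8.
- NOAR = 60. Non-operative or negative appendicectomy = 60 + 8 = 68.

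**3. Swaps that leave the number of admissions unchanged**

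| Change per 100 admissions | NOAR | NOAR plus negative appendicectomy |
|---|---|---|
| None | 60 | 68 |
| All 8 spared, observed overnight | 68 | 68 |
| 8 more normal appendices removed from observed patients | 52 | 68 |

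The 8-point rows are bounds, not forecasts. With a non-operative share of 50% or 70%, sparing all normal appendices with observation moves NOAR from 50 to 60 or from 70 to 76.

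If the 8 spared patients go home instead, NOAR is 60/92 = 65.2% with admitted patients as denominator, and unchanged with all attenders as denominator. The definition can be read either way. The two swaps in the table move NOAR in the same direction under both readings.

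**4. Effect on power when spared operations become observation**

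True fall to 45%, offset by x points:
- x = 2: 0.60 v 0.47, power 0.82.
- x = 4: 0.60 v 0.49, power 0.68.
- x = 8 (bound): 0.60 v 0.53, power 0.34.

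**5. The supporting outcome at the planned size**
- In every case in step 4 the combined outcome goes from 68 to 45 + 8 = 53, because the swap does not touch it. Power for 0.68 v 0.53 is 0.92.
- If it fell by 25% in relative terms, 0.68 to 0.51, power would be 0.97.
- Both figures assume that the ICC of 0.06 carries over.

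**The case against.** The strongest reply is that the protocol deliberately separates two targets. Its Potential Impact list, the rationale for implementation research, the objectives and the description of the package all name unnecessary admission and unnecessary surgery side by side, with NOAR as the main objective and surgery as a secondary one. This stands in part: it would be too much to infer that the protocol consistently counts negative appendicectomy as unnecessary admission. It does so in two places. The mismatch between the summary label and the operational definition remains on either view.

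The second reply is that a shift would be visible. Negative appendicectomy is a secondary outcome, days alive and out of hospital counts hospital time with or without surgery, and histological features of inflammation are examined to support the primary outcome. This also stands in part, since a large shift would probably be noticed. But the negative appendicectomy rate has operated patients as its denominator, a group the package may itself change, so it cannot be netted against NOAR. No joint reading of the two is stated. The protocol defers a full SAP, which is not at hand and could add one; the definition and its label, however, are fixed in the protocol.

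A reader might infer that the package could succeed by increasing unnecessary surgery. The documents do not support that. They associate imaging and risk stratification, which the programme teaches, with fewer negative appendicectomies. The more plausible swap is from surgery to observation. It works against the trial's own claim and would not create a false positive.

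A reader might also judge these shifts against a lower baseline, say 30%, where the target is only 7.5 points and they look twice as large. That baseline gives power of about 0.47 in the stated design, so it does not fit the protocol's 0.90.

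**Conclusion.** The point holds as a mismatch between label and endpoint, with a moderate and conditional effect on interpretation. Per 100 overnight admissions, about 8 negative appendicectomies lie outside NOAR (10 to 6 for a non-operative share of 50% to 70%), against a target fall of 15 points. An offset of 2 to 4 points from spared surgery turned into observation would cut power from 0.91 to between about 0.82 and 0.68. How large the offset will be cannot be known from the documents.

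These figures rest on the assumptions listed in the working, chiefly the 60% baseline and that all operations in admitted patients are appendicectomies. The direction of the two swaps does not depend on them: an operated patient is never in the numerator.

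The finding does not show that the sample size is wrong or that NOAR must be replaced as the primary outcome.

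**What to change.** 1. Keep NOAR as primary. In the summary, describe it as overnight admission without an operation instead of unnecessary overnight admission.
2. In the outcome section, add a pre-specified supporting outcome: overnight admission with no operation, or with a negative appendicectomy on histology. Analyse it with the same model and population as NOAR.
3. Report negative appendicectomy per included patient as well as per operated patient.
4. State that a NOAR reduction will be read as fewer unnecessary admissions only alongside the effect estimates and confidence intervals of these two outcomes.

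A rule that NOAR and the supporting outcome must move in the same direction is not advised. A pure swap between observation and negative appendicectomy leaves the supporting outcome unchanged in expectation, so chance would decide the rule. The supporting outcome also gives a night's observation the same weight as removal of a normal appendix, which is why item 3 is needed beside it.

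Cost: a change of wording and one or two extra models. Histology is already collected for the negative appendicectomy outcome. Operated patients whose histology is still pending at 30 days would need the missing-outcome handling already planned.
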